4.4.3 Adjustment for Covariates

All efficacy analyses will be adjusted for covariates as described in Section 4.4.2. These will include the corresponding baseline value and re-derived age at first dose (in years and months) as covariates, and concomitant steroid use as a factor. Additional covariates will also be included for the following baseline values where appropriate (see Section 4.4.2): 4SC, time to rise from floor, time to run/walk 10 metres, distance walked in 6 minutes (for the analysis of percent predicted 6MWT, this will be replaced with baseline percent predicted distance walked in 6 minutes).

4.4.4 Handling of Missing Data

4.4.4.1 Classification and Imputation

For the efficacy analyses, any missing data for continuous values for a subject will be classified as follows:

1. the subject has missing data due to reasons other than being non-ambulatory or physically unable to perform the test / assessment
2. the subject has missing data due to being either non-ambulatory or otherwise physically unable to perform the test / assessment.

Any missing values classified as 1 will be imputed using the mean of all non-missing values for the respective measurement and timepoint across all subjects randomised to the respective treatment and in the respective concomitant steroid stratum and Group (i.e. Group A, target population or Group B, off-target population).

Any missing values classified as 2 will be imputed by setting the value to zero or to twice the maximum non-missing value recorded across all subjects depending on the directionality of the test.

In all cases, imputation of any data classified as 1 will be completed first, followed by imputation of any data classified as 2.

Classification and imputation of missing data will be completed prior to any transformation of the data for analysis. For example transformation of the timed function test results for presentation of velocity or any log transformation applied as needed (per Section 4.4.2).

For binary or time to event variables where missing data means that the binary response or time to event cannot be determined, the missing data from which the variable is derived (e.g. 6MWT values) will first be classified and imputed, as described above, in order to then derive the binary response or the time to event. Exceptions to this are where the criteria for deriving the binary response themselves refer to presence of missing data, for example loss of ambulation. The classification described above will be used for the relevant missing data in these cases in order to confirm physical inability to complete the respective test. Further details are given below regarding the rules for derivation of the binary endpoints in the presence of missing data.

For the NSAA assessment, where the total score is a sum of ordinal item scores, imputation of Class 1 and Class 2 data will follow a different approach as defined in Appendix 7.5.4.

The rules for classifying missing data from the responses on the eCRF and any additional considerations for imputation are given in Appendix 7.5 for each respective endpoint. Unless otherwise stated, only the value of interest for analysis will be classified and imputed. For example, the 'duration' for the 4SC assessment will be imputed but not the 4-stair ascent grading.

Note that missing data at any scheduled timepoint should be imputed according to the above rules. This includes any scheduled timepoints after a subject withdraws early. In these cases, where the final assessment prior to withdrawal was missing and determined to be Class 2 missing data, all missing assessments post withdrawal will also be considered Class 2. Otherwise, these will be considered Class 1. Note that where this applies to an NSAA assessment, 'Class 1' will refer to the scenario where

'Was assessment attempted?' = 'No'. Where a date of assessment is required, the predicted date for imputed timepoints post withdrawal will be used. The same approach will be followed for any completely missing visits prior to withdrawal or completing the study, where no information has been entered into the respective CRF assessment page indicating whether or not it was performed.

Where data entered into the CRF for an assessment are ambiguous such that they do not reflect any of the expected responses outlined in Appendix 7.5 and therefore missing data cannot be classified, a worst case approach will be followed and the missing data will be assumed Class 2.

A review will be performed at the BDRM to confirm correct classification of missing data. This may identify data entered into the CRF assessment page which comply with Appendix 7.5 but additional information is available to contradict the classification (for example in comments). Any such cases will be assessed on a case by case basis to determine the appropriate classification to be applied.

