2.7 Changes from the Protocol Planned Analysis

The pharmacokinetic analysis set has been introduced.

The exploratory endpoint "Time to loss of standing (Baseline through end of study)" has been updated to clarify that this is the time to *persistent* loss of standing in order to allow time for recovery due to trauma. Additional clarity has also been added regarding how this endpoint is derived.

The exploratory endpoint "Proportion of subjects with $\geq 10\%$ worsening in 6MWT at the end of the study" has been updated to clarify that this is the proportion of subjects with

≥10% *persistent* worsening in 6MWT at the end of the study. Additional clarity has also been added regarding the definition for inclusion of subjects in this proportion.

In addition, exploratory subgroup and supplementary analyses have been included in this SAP.

Summary and analysis of results of the DMD serum biomarker assessment and any relationship with treatment effect will not be included as part of this SAP but in a separate dedicated SAP.

The presentation of data on the target and/or overall subject populations has been streamlined to ensure the most appropriate population is used for each data type, with the option to include additional repeats post hoc if required.

Additional criteria have been added to the definition of the Intent-To-Treat (ITT) analysis set to ensure that subjects included in this population have received at least one dose of study drug and have at least one post-baseline 4SC measure, or alternatively a missing 4SC measure due to being either non-ambulatory or otherwise physically unable to perform the assessment (as this still provides useful information regarding disease progression). This was felt appropriate to ensure a suitable population for the primary analysis.

The text for the analysis set definitions has been updated slightly to clarify the difference between the analysis sets themselves (defined by the analysis set criteria) and the subdivision into target/overall populations (defined by baseline MRS VL MFF results).

The definition for the MR cohort has been updated to clarify that subjects must complete at least one post-baseline MRI/MRS assessment to be included as this cohort is to be used for presentation of MRI and MRS data.

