3.1.1 Analysis Sets

The **All enrolled subjects** set for the target population will include all subjects in the target population who were randomised to study treatment. The all enrolled subjects overall set will include all subjects in both the target and off-target populations (Group A + Group B) who were randomised to study treatment.

The **Intent-To-Treat (ITT)** analysis set for the target population will include all subjects in the target population who are randomised, who receive at least one dose of study drug and who have at least one non-missing post-baseline 4SC measure or missing post-baseline 4SC measure due to being either non-ambulatory or otherwise physically unable to perform the assessment, irrespective of any deviation from the protocol or premature discontinuation. The treatment group assignment will be designated according to initial randomisation. The ITT analysis set in the target population will serve as the basis for the formal analysis of efficacy. The ITT analysis set for the overall population will include all subjects in both the target and off-target populations who are randomised, who receive at least one dose of study drug and who have at least one post-baseline 4SC measure or missing post-baseline 4SC measure due to being either non-ambulatory or otherwise physically unable to perform the assessment, irrespective of any deviation from the protocol or premature discontinuation. The ITT analysis set in the overall population may be used for any supportive efficacy analyses.

The **Safety (SAF)** analysis set for the target population will include all randomised subjects in the target population who receive at least one dose of the study drug. The treatment group assignment in this analysis set will be defined by the treatment actually received. This will be used for any evaluation of safety in the target population. The SAF analysis set for the overall population will include all randomised subjects in both the target and off-target populations who receive at least one dose of study drug. This will be used for evaluation of safety in the overall population.

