The **Pharmacokinetic** (PK) analysis set for the target population will include all subjects in the target population who have received at least one dose of treatment with givinostat and who have at least one post-dose concentration of study drug. The PK analysis set in the target population will be used for all formal PK summaries and analyses. The PK analysis set for the overall population will include all subjects in both the target and off-target population who have received at least one dose of treatment with givinostat and who have at least one post-dose concentration of study drug. The PK analysis set in the overall population may be used for any supportive PK evaluations. Final membership of the PK analysis set in both the target and overall populations will be confirmed after unblinding.

The **Magnetic resonance** (MR) cohort includes all subjects in the target population who were randomised to study treatment and completed at least one post-baseline MRI/MRS assessment. These subjects will be expected to perform the magnetic resonance assessment at baseline, 12 and 18 months. Therefore, this cohort will form the basis for analysis of all MRI/MRS parameters.

The definitions for all the above analysis sets are sufficient to determine the subjects included and there will be no requirement for formal review and approval of population membership by Italfarmaco.

Membership to each of the above analysis sets will be determined programmatically based on the data collected and in line with the defined criteria above. The assignment of subjects to each of the analysis sets, except for the PK analysis set, will be determined prior to unblinding, once all study data are available for the respective analysis. For the PK analysis set, final membership to this set will be confirmed following unblinding and will again use programmatic derivations without the requirement for manual review.

All enrolled subjects will be listed indicating their membership to each analysis set along with the reason for exclusion. A listing will also present details of any randomisation code breaks.

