The need for a possible log transformation of these variables will be investigated prior to unblinding by assessing the ANCOVA model residuals without a treatment term. Where data are transformed for analysis, back transformation will be applied for the presentation of results. Presentation of the tables will be amended as needed for this, for example with the addition of an explanatory footnote.

Analysis of cumulative loss of function on the NSAA over 18 months of treatment with givinostat or placebo will be performed using negative binomial regression. The dependent variable will be the subject cumulative number of failures across all post-baseline visits. Total failed items at baseline, baseline values for: 4SC, time to rise from floor, time to run/walk 10 metres, distance walked in 6 minutes and re-derived age at first dose (in years and months) will be included as independent covariates in the model, with randomised treatment group and concomitant steroid use included as independent classification factors. The estimated cumulative number of failures across 18 months and associated 2-sided CIs from the model will be presented for each treatment group. The treatment effect will be presented as the ratio of cumulative failures for givinostat relative to placebo along with the associated 2-sided CI and p-value, where a lower ratio indicates a greater reduction in cumulative number of failures across 18 months for givinostat compared with placebo.

The binary efficacy variables (proportion of subjects with $\geq 10\%$ persistent worsening in 6MWT, proportion of subjects losing ambulation during the study) will be analysed using logistic regression. In each instance baseline values for: 4SC, time to rise from floor, time to run/walk 10 metres, distance walked in 6 minutes and re-derived age at first dose (in years and months), will be included as independent covariates. Randomised treatment group and concomitant steroid use will be included as independent classification factors. The odds ratio comparing the treatment groups will be presented, together with its associated 2-sided CI and p-value.

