4.4.4.2 Analysis

Once classified and imputed, the following procedures will be applied for the analysis of endpoints where there are missing data with imputation. The approach will be dependent on the class(es) of missing data present and also the directionality of the test where Class 2 missing data are present. Any analysis of binary or time to event variables with missing data, or the cumulative loss of function on the NSAA, will use the appropriate procedure described in Section 4.4.2, following any classification and imputation per the methods above. Thus, the below procedures apply only to the continuous variables.

Note that where the endpoint to be analysed is a change from baseline, any imputation (per the following procedures) will be applied to the observed values prior to finding the corresponding change from baseline.

Variables with only Class 1 missing data

For the following variables, only Class 1 missing data will be applicable:

- VL MFF determined by MRS
- PODCI standardised scores for each subscale and the global function scale, as completed by the parent and the subject
- Fat fraction in 5 thigh muscles as determined by MRI
- Cross-sectional area of 5 thigh muscles as determined by MRI
- Any other variable where all missing values have been classified as 1 and no Class 2 missing values have been identified.

Any missing values will be imputed as per the rules for Class 1 missing data and the applicable analysis will be performed as described in Section 4.4.2 and Sections 4.1 to 4.3.10 as relevant to the respective variable.

Variables with any Class 2 missing data where higher values are worse

For the following variables, the directionality is such that higher values represent a worse outcome:

- 4SC
- Time to rise from the floor
- Time to run/walk 10 metres

If any Class 2 missing data are identified for these variables, the analysis of the variable will be performed as follows:

If x_{ijk} represents the value of the variable to be analysed for subject i randomised to treatment j at time k , then missing data will be imputed as

Class 1: $x_{ijk} = \bar{x}_{jk}$ where \bar{x}_{jk} is the mean of all non-missing values for the respective measurement at time k across all subjects randomised to treatment j and in the respective concomitant steroid stratum and Group (i.e. Group A, target population or Group B, off-target population).

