Class 2: $x_{ijk} = 2 \times \text{Max}(x)$ where $\text{Max}(x)$ is the maximum non-missing value recorded for the variable across all subjects, regardless of treatment, stratum or Group.

Following the assignment of imputed values, the data x_{ijk} will be analysed as described in Section 4.4.2 and Sections 4.1 to 4.3.10, as relevant to the respective variable using PROC MIXED, ensuring that reference levels are stated for all class variables so that difference in LSmeans is calculated as givinostat-placebo. F-tests from PROC MIXED will be based on Kenward-Roger's adjusted degrees of freedom.

LSmeans for drug and placebo from this model, denoted \bar{x}_D and \bar{x}_P respectively, the difference in the LSmeans, $\bar{x}_D - \bar{x}_P$, and the associated 2-sided CI and p-value will be taken from the LSmeans statement in PROC MIXED.

Note that for the analysis of these variables on the transformed scale representing velocity rather than time, transformation will be applied to the imputed data x_{ijk} to give the velocity values u_{ijk} used in the analysis model described above. The results from the model will be presented on the transformed scale without back transformation and will be interpreted as estimates of velocity.

Variables with any Class 2 missing data where lower values are worse

For the following variables, the directionality is such that lower values represent a worse outcome:

- 6MWT
- Percent predicted 6MWT
- NSAA
- Muscle strength evaluated by knee extension and elbow flexion as measured by HHM.

If any Class 2 missing data are identified for these variables, the analysis of the variable will be performed as follows:

If x_{ijk} represents the value of the variable to be analysed for subject i randomised to treatment j at time k , then subjects with missing data will be imputed as

Class 1: $x_{ijk} = \bar{x}_{jk}$ where \bar{x}_{jk} is the mean of all non-missing values for the respective measurement at time k across all subjects randomised to treatment j and in the respective concomitant steroid stratum and Group (i.e. Group A, target population or Group B, off-target population).

Class 2: $x_{ijk} = 0$

The exception to this is the NSAA total score which will be derived from imputed item scores as described in Appendix 7.5.4.

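### Class 1 gaps are filled with one fixed mean and analysed as measured, so the stated error level and interval coverage for 4SC and the continuous key secondary endpoints other than NSAA total are not guaranteed

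*SAP*

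**What the plan says.** SAP 4.4.4.1 splits missing continuous values into Class 2 (non-ambulatory or physically unable) and Class 1 (any other reason). For Class 1: "Any missing values classified as 1 will be imputed using the mean of all non-missing values for the respective measurement and timepoint", within the same arm, steroid stratum and Group. The rule extends to scheduled visits after early withdrawal. SAP 2.9 also puts COVID-19 gaps in Class 1. Class 2 values become twice the recorded maximum for timed tests, and zero for tests where low is worse.

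Under SAP 4.4.4.2 the fill comes before change from baseline is computed, and "the associated 2-sided CI and p-value will be taken from the LSmeans statement in PROC MIXED". No variance correction is described for the formal analysis. NSAA total is an exception: Appendix 7.5.4 fills its items with modes or zeros.

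Three further rules determine how many values are filled:

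- For VL MFF, SAP 4.4.4.2 states: "For the following variables, only Class 1 missing data will be applicable". But the MR cohort (SAP 3.1.1) takes only target-population boys "who were randomised to study treatment and completed at least one post-baseline MRI/MRS assessment".
- For 4SC, the ITT set keeps boys "who have at least one non-missing post-baseline 4SC measure or missing post-baseline 4SC measure due to being either non-ambulatory" or otherwise physically unable, so a boy with no 4SC data for other reasons leaves the analysis.
- Where the eCRF entry is ambiguous, "a worst case approach will be followed and the missing data will be assumed Class 2".

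SAP 4.4.4.3 adds a tipping-point analysis of 4SC using Rubin's rules, run only if the primary result is significant. The SAP addendum does not change the rule for these endpoints.

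**The concern.** A filled value adds to the sample size and the degrees of freedom, but it carries no new information and almost no residual scatter. The model cannot tell it from a measurement, so Kenward-Roger degrees of freedom do not help. The standard error comes out too small even when data are missing completely at random, so the missing-at-random premise does not rescue it. At stake are the nominal level of the 4SC test, the Hochberg tests of the affected key secondaries, and the coverage of their intervals.

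**Working it through.** **The plan's own figures (SAP 2.5).** With 2:1 allocation, the placebo number is 1.5 × (1.960 + 1.282)² × SD²/Δ². With Δ = 2 s and SD = √(3.094² − 1²) = 2.928, this is 1.5 × 10.507 × 8.573/4 = 33.8, so 34 + 68 = 102, as stated. It reproduces only if 3.094 is the overall SD, as the protocol synopsis calls it. SAP 2.5 calls it within-treatment, which would give 38 + 76 = 114. That is a separate matter. Dropout: 102/0.92 = 110.9, against 110 stated; 110 × 0.92 = 101 boys observed. The 8% is total dropout, not a Class 1 share.

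**Closed-form approximation, Class 1 only.** Let m be the filled share. The treatment difference is about what the observed boys give. The residual sum of squares hardly grows but is divided by about N instead of N(1 − m), and the variance of a mean uses N instead of N(1 − m). The model SE is therefore about (1 − m) times the true SE, and the true two-sided error is 2[1 − Φ(z(1 − m))].

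| Nominal level | m = 3% | m = 5% | m = 8% |
|---|---|---|---|
| 0.05 (z = 1.960) | 5.7% | 6.3% | 7.1% |
| 0.05/2 (z = 2.241) | 3.0% | 3.3% | 3.9% |

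The second row shows one stricter Hochberg step. Family-wise error was not computed.

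**Simulation under a null effect.** Inputs: 110 boys (73 vs 37), four strata, ANCOVA with the planned covariates, Class 1 missing at random. Assumed, because the documents do not give them: stratum shares, baseline distribution, mean decline, correlations, and the Class 1 and Class 2 counts. The 18-month 4SC change SD was about 3.09 s. The main runs used 20,000 trials per cell (±0.3 to 0.4 points); confirmatory runs used 6,000 (about ±0.6).

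*4SC, no Class 2.* The main runs gave 5.5 / 6.5 / 7.3% at 3 / 5 / 8% Class 1. Model SE against true SD was 0.605/0.620, 0.603/0.635 and 0.598/0.656, that is 2, 5 and 9% too small. Runs with other assumptions gave 5.0-5.6%, 6.1-7.0% and 7.0-7.6%, skewed times included.

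*4SC, with Class 2.* The twice-maximum values inflate the residual variance and mask the excess. With 2 / 6 / 11 Class 2 boys the main runs gave 5.2 / 5.2 / 5.2% at 3% Class 1, 5.6 / 5.2 / 4.9% at 5% and 6.1 / 5.2 / 5.0% at 8%. A second set at 8% gave 6.2 / 6.0 / 5.6%. The two sets differ by more than Monte Carlo error at 6 and 11 boys, so only the range should be relied on. Skewed times with some Class 2 gave 4.6-5.2%. The confirmatory runs with 2 to 6 Class 2 boys gave about 4.4-6.6%. SAP 4.4.2 leaves the scale open ("The need for a possible log transformation of these variables will be investigated prior to unblinding"); after a log transformation the masking is weaker, at 5.3-6.7%.

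*VL MFF.* The 18-month change SD was assumed equal to the 12-month 5.941%, with 8% dropout spread evenly over 18 months and boys without any post-baseline scan removed.

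| Early-withdrawal scan done in | Imputed share | Error | Model SE / true SD |
|---|---|---|---|
| none | 2.8% | 5.8% | 1.256/1.288 |
| half | 5.5% | 6.5% | 1.233/1.306 |
| all | 8.0% | 7.3% | 1.211/1.322 |

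*Is the fill the cause?* The same ANCOVA without the Class 1 boys rejected in about 4.2-5.3% of null trials across all runs (5.0% for VL MFF). Multiple imputation on treatment, stratum and the analysis covariates (20 imputations) gave 4.9% for 4SC at 8% Class 1 with no Class 2.

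**The case against.** **The primary endpoint may be barely affected.** DMD is progressive, so some Class 2 values are likely, and with them most 4SC results lie close to 5%. The ITT rule, the worst-case rule for ambiguous entries and the retention of late month-18 visits as measured all keep the Class 1 share down. This stands, and it limits the claim for 4SC. But the masking is a by-product of extreme values whose number is unknown when the rule is fixed, and COVID-19 gaps push the Class 1 share up.

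**The tipping-point analysis already covers it.** A false positive can arise only after a significant primary result, which is exactly when this analysis runs, and its unshifted step is a Rubin's-rules result (4.2-5.1% in simulation). That is a genuine check for 4SC, and it would expose a fragile result. It does not change the formal p-value or interval, and it does not reach the secondaries.

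**The secondaries are not tested at 5%.** Correct: they are judged at 0.05/i by Hochberg rank, so the simulated VL MFF figures apply directly only at rank 1. The SE is too small at every rank.

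**The MR cohort rule limits VL MFF.** It does ("subjects must complete at least one post-baseline MRI/MRS assessment to be included"): a boy who withdraws without any post-baseline scan is never filled. The VL MFF figures allow for this.

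**Conclusion.** The mechanism is certain from the text; its size is not. For 4SC and the continuous key secondaries other than NSAA total (time to rise, 6MWT, knee extension, elbow flexion, VL MFF), the model SE ignores Class 1 imputation uncertainty, so the stated level and coverage are not guaranteed. At a nominal 5% test, under a null effect and Class 1 missing at random:

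- no Class 2 values: about 5-5.5% at 3% Class 1, 6-7% at 5%, 7-7.5% at 8%;
- VL MFF in the MR cohort: 5.8-7.3%, with nothing to mask it;
- 4SC with some Class 2 values: about 4.5-6.5%, often near nominal.

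A reader might infer that the primary test really runs at 7% or more. The documents do not support that: it would need all 8% planned dropout to be Class 1 and retained in the ITT set, with no Class 2 boys. Nor should the point be extended to every key secondary, since NSAA total follows a different rule. This should be fixed; it does not by itself overturn a clear result.

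**What to change.** In SAP 4.4.4.1 and 4.4.4.2, for 4SC and the continuous key secondaries other than NSAA total, stop treating Class 1 mean-filled values as observed in the formal analysis.

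1. Use multiple imputation under missing at random, combined by Rubin's rules. The imputation model should hold treatment, steroid stratum, all covariates of that endpoint's analysis model and the earlier observed visits.
2. Impute timed tests on the log scale, or with a positive lower bound, and back-transform. Otherwise times at or below zero can occur, and the log and velocity analyses break down.
3. Where an Early Withdrawal test is used, do not discard it in favour of an older visit; keep the latest observed value.
4. Assign the SAP's Class 2 value within each completed dataset.
5. Keep mean imputation as a sensitivity analysis.

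A simpler alternative that also holds the level is the planned ANCOVA without the Class 1 boys. Like the present rule, both options assume that Class 1 boys could still do the test.

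Cost: SAP wording and modest programming (PROC MIANALYZE is already planned in 4.4.4.3). For multiple imputation, SAP 2.8 also needs an exception, because it carries imputed values into every presentation. Intervals widen slightly. At 8% Class 1 and no Class 2, the 4SC standard error is about 0.62-0.65 instead of 0.60-0.61; for VL MFF it is about 1.26 instead of 1.21-1.26. These come from multiple imputation on the raw scale, which held 4.8-5.5% for 4SC and 4.9-5.0% for VL MFF. Points 2 and 3 were not simulated, so the final specification should be checked before adoption.
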